## RESEARCH METHODS

### A. Outcome Measure(s)

**Study Aim 1:** Our primary outcome for **Aim 1a** is rates of viral suppression (defined as VL <1000 copies/mL) at 12 months after enrollment for each child at the study facilities. Our secondary outcomes for Aim 1 are VL suppression and DRM patterns up to 5 years and time to viral suppression among those children without viral suppression at their 1st POC VL testing or newly initiating ART after POC VL testing implementation. We will also examine a set of process outcomes in this study, such as the feasibility of POC VL testing by describing the uptake, which we define as the proportion

of children undergoing VL testing within each group at the scheduled intervals. We will also examine the turn-around time for the VL testing results, retention-in-care, proportion of children switching ART, time to switch to 2nd or 3rd line ART, etc. for each arm. We hypothesize viral suppression rates will be higher among children with access to POC VL testing and time to viral suppression shorter compared to children with standard VL testing in the control arm one year after POC VL testing implementation. In **Aim 1b**, we intend to validate HIV-1 POC VL testing against current in-country gold standard VL testing by generating concordance/discordance rates and Cohen's kappa to determine assay agreement. We will also conduct sensitivity analyses to the concordance rates at lower thresholds of viral load cut offs for viral suppression (down to <40 copies/mL, the lower limit of quantification for the POC VL testing).

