For those assigned to the control arm, VL testing will be conducted per national guidelines (as outlined above) through laboratory networking and transport to a centralized laboratory as the SOC. Children in the SOC arm who are newly initiating ART will have blood collected prior to ART initiation for future VL and DRM testing to be conducted at completion of study follow up. These results will be returned to clinical providers and patients/caregivers after the study. Additionally, in order to have comparable outcomes, POC VL will be conducted on ALL SOC participants at 12 and 24 months of follow up. Study nurses will prompt providers to order follow-up VL tests for those who qualify to ensure uptake of VL testing in both study arms.

We will batch test all stored samples for gold standard VL testing towards the end of the study period for both the arms (n= up to 700 samples), and generate concordance/discordance rates and Cohen's kappa to determine assay agreement. We will also conduct sensitivity analyses to the concordance rates at lower thresholds of viral load cut offs for viral suppression (down to <40 copies/mL, the lower limit of quantification for the POC VL testing). To conduct the in-country

gold standard HIV-1 VL testing (or quantification), we will build on our existing partnership with the KEMRI-CDC HIV Research Laboratory, led by [name], a collaborator on this proposal. The KEMRI-CDC facilities are located immediately outside of Kisumu. The KEMRI-CDC HIV Research laboratory utilizes state of the art HIV-1 quantification technologies by using Abbot m2000sp/RT, Roche CAP/CTM, and Roche C8800 systems (cite). Overall, the two main assay platforms, the Abbot vs. the Roche platforms, both perform extremely well, with subtle difference in accuracy and precision of each platform (cite). As we get closer to the time of running our samples for this validation, we will determine which specific platform to use depending on logistical aspects, such as current usage of the platforms. These platforms can run the assays with 0.5-1mL of plasma, which will already be stored in cryovials of this volume at the same facility. For each sample analyzed, we will receive printed reports noting exact quantification or below or above the limits of quantification.

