Power for the study is based on the primary outcome of proportion of VS in children in the intervention vs. control arms at 12 months after enrollment for each child (Aim 1). We estimated requiring a sample size of 90% (630) of an estimated 700 children eligible to enroll to have 80% power to detect an effect size of a difference between arms of at least 11%. Accounting for 10% loss to follow-up over 12 months, this sample size is expected to provide total of 567 children (or 284 per arm) with outcomes for analysis. These calculations are based on Fisher's exact test, two-sided $\alpha=0.05$, and initial VS rates of approximately 65% (estimated from historical facility data).

Table 5: Effect sizes and power calculations				
VS rates, control (SOC) vs. intervention (POC) arms	Difference (effect size)	Power	Expected Total N for analysis	Expected N per arm for analysis
65% vs. 70%	5.0%	0.22	567	284
65% vs. 72.5%	7.5%	0.45	567	284
65% vs. 75%	10%	0.71	567	284
65% vs. 76%	11%	0.80	567	284
65% vs. 77.5%	12.5%	0.89	567	284
65% vs. 80%	15%	0.98	567	284
70% vs. 80%	10%	0.76	567	284
70% vs. 82.5%	12.5%	0.93	567	284
70% vs. 85%	15%	0.99	567	284

A power calculation was also performed for how precisely the prevalence of DRMs could be estimated. With 284 participants randomized to the intervention arm, we expected approx. 35% (100) to not achieve VS at their 1st POC VL test and undergo DRM testing, and we would be able to estimate prevalence of DRMs to within +/- 5% to 10% of the 95% CIs. For example, for a class of DRMs with prevalence of 80%, we anticipate generating exact 95% CIs of 71.3%-87.0%; a less common DRM at 10% will generate 95% CIs of 5.1%-17.1%.

Outcome Variables

Aim 1 primary outcome

Our study's primary outcome is the child's VS (defined as $VL < 1000$ copies/mL) at 12 months after enrollment (defined as from a blood draw within 12 months +/- 16 weeks after the enrollment date). VL quantity is determined using results from the study's POC HIV VL GeneXpert test result which was planned for both randomization groups at the 12-month time point. Where a participant has no POC result available at 12 months but does have a standard laboratory VL available at 12 months, the standard laboratory VL is used. A month is considered to be 28 days.

Aim 1 VL sensitivity analysis outcomes

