While not our primary outcome, interim descriptive statistics of VLs over time are provided for VS at baseline and quarterly thereafter. For participants in the POC group, POC test results are used. For participants in the SOC group, SOC test results are used. Testing over time is shown descriptively using testing intervals defined by days since enrollment: Enrollment = 0-2 years prior to enrollment; 3 months = 1 day to 3 months + 6 weeks after enrollment; 6 months = 6 months +/- 6 weeks; 9 months = 9 months +/- 6 weeks. This could differ from study visits as assigned by visit staff, for example if a 6 visit was attended over 6 weeks late it could fall in the 9-month interval. If more than one test had been performed in an interval, the test closest to the target date is used.

Study Aim 1. Effect of the intervention:

All analyses of the effect of the intervention are ITT, using randomized group assignment as the exposure variable as described in the Exposure Variables section (p3).

Aim 1a: We hypothesize that the proportion with VS one year after enrollment will be higher among children randomized to POC VL testing compared to those in the control group. Our primary analysis will compare the proportion of children with VS 12 months after enrollment as defined by our primary outcome in the intervention vs. control groups, estimating the RR for the intervention effect using a modified Poisson regression model with robust standard errors, adjusting for facility and age group strata (1-9 or 10-14 years). We provide supporting descriptive statistics of the primary outcome by randomized group. Sensitivity analyses using lower cutoffs for VS follow the same methods as the primary analysis except outcomes are as specified for sensitivity analyses of the primary outcome; they present an *a priori* sensitivity analysis comparing VS at 12 months defined as <40 copies/mL. A *post hoc* sensitivity analysis defines VS at 12 months as <400 copies/mL.

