Subgroup analyses for the effect of the intervention will examine potential effect modification by age group (1-9 years old or 10-14 years old) using the same model as the primary analysis and including an interaction term between age group and intervention group in the model. While the study is not powered to test the intervention effect within age subgroups, particularly in the subgroup of 10-14 year-olds, this analysis will provide data for the intervention effect within each, as well as for any difference in effect between the younger and older children. Gender, time on ART (< 2 years, 2-5 years, or >5 years), VS status of the caregiver, and whether the caregiver is the biological parent are also *a priori* subgroup variables considered for effect modification, in each case by adding the main effect of the subgroup variable and the interaction term between subgroup variable and randomization group.

Aim 1b: we hypothesize that among children newly initiating ART or initially unsuppressed, the proportion with VS one year after enrollment will be higher among children randomized to POC VL testing compared to those in the control group. The analysis among children newly initiating ART or initially unsuppressed will follow the same methods as the primary analysis to compare the proportion of children with VS 12 months after enrollment as defined by our primary outcome except that VS will be defined as <400 copies/mL and the analysis will be limited to the population of children meeting our definition of newly initiating ART or initially unsuppressed. Children newly initiating ART are defined as those initiating ART within 30 days of study enrollment. Children initially unsuppressed are those with VS ≥ 400 copies/mL. for the POC group, at the initial POC VL test. Because in SOC only a subset were tested at enrollment, we used first VL test up to and including 6 months to identify SOC children who were initially unsuppressed (i.e., from enrollment testing interval to 6 month testing interval).

Subgroup analyses for the effect of the intervention among children newly initiating ART or initially unsuppressed are conducted for subgroups defined by age group, and for subgroups defined by children newly initiating ART vs. those already on ART but initially unsuppressed. For each, the effect of the intervention within subgroups is estimated by including the appropriate main effect and interaction term in the model.

Other associations with VS

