POC group was not consistently performed quarterly due to COVID interruptions either delaying or preventing in-person visits, especially at study months 6 and 9. Also, for SOC children, the routine testing schedule did not necessarily align with study enrollment, resulting in SOC VLs performed at enrollment only for a subset of SOC children, and subsequently, SOC was not necessarily performed quarterly. Because in neither arm was time to VS measured consistently, we changed from comparing time to VS by estimating a hazard ratio from Cox regression, to comparing VS at 12 months by estimating a relative risk from a modified Poisson regression so that our outcome is measured in the same manner in both groups. Second, because in SOC only a subset were tested at enrollment, we used first VL test up to and including 6 months to identify SOC children who were initially unsuppressed. Third, we defined the cutoff for being initially unsuppressed and for achieving VS after enrollment to be based on 40 copies/mL to allow us to explore the question of value of our intervention in those not clearly initially suppressed. After unblinding, we discovered that enrollment VL data in those with both POC and SOC tests showed that POC tests missed a noticeable number of those with $VL > 40$ by SOC, but not in those with $VL > 400$ copies/mL; to reduce any bias from differences in the tests we changed our plan to use a cutoff of 400 copies/mL both for identifying initially unsuppressed children and for the VS outcome at 12 months for this analysis.

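### The Aim 1b cut-off of 400 copies/mL was adopted after unblinding, but the Aim 1b analysis text carries no post hoc label and plans no result at another cut-off

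*SAP*

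**What the plan says.** Aim 1b here follows the SAP's numbering; the protocol uses that label for assay validation.

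- **Protocol, A. Outcome Measure(s).** The primary outcome, for all children, is "rates of viral suppression (defined as VL <1000 copies/mL) at 12 months after enrollment". For children unsuppressed or initiating ART, the protocol planned time to suppression, analysed with a Cox model (F. Data Analysis Plan).
- **SAP, Changes to the analysis plan, Study Aim 1b.** Before unblinding, the Cox model was replaced by a 12-month risk ratio, and a cut-off was set: "Third, we defined the cutoff for being initially unsuppressed and for achieving VS after enrollment to be based on 40 copies/mL". After unblinding, enrollment samples with both tests showed POC missing values above 40 that the laboratory test found, but not values above 400. The SAP then reports: "we changed our plan to use a cutoff of 400 copies/mL", for entry and outcome alike.
- **SAP, Study Aim 1, Aim 1b.** The hypothesis is stated and the primary-analysis methods are applied "except that VS will be defined as <400 copies/mL". Nothing there says the cut-off is post hoc or points to the changes section.
- **SAP, Study Aim 1, Aim 1a.** The same cut-off is expressly called post hoc: a "sensitivity analysis defines VS at 12 months as <400 copies/mL". The <40 version is called a priori.
- **SAP, Aim 1 VL sensitivity analysis outcomes.** Alternative cut-offs are defined for the primary comparison only.
- **SAP, Aim 1 primary outcome.** The 12-month value is the "GeneXpert test result which was planned for both randomization groups at the 12-month time point"; if it is missing but a laboratory result exists, "the standard laboratory VL is used". The protocol (Study methods) likewise says "POC VL will be conducted on ALL SOC participants at 12 and 24 months of follow up".

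**The concern.** A threshold fixed after unblinding is written into the section that tests a stated hypothesis, under a general significance level of 0.05. A reader of that section alone would take it as prespecified, although the SAP labels the same number post hoc one aim earlier. The two Aim 1b subgroup analyses inherit the cut-off.

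The stated reason fits one of its two uses better than the other. Entry is classified by different tests in the two arms, so disagreement near 40 could select different kinds of children. The 12-month outcome is planned on one test in both arms. With no Aim 1b result planned at any other cut-off, nobody could see whether the conclusion depends on the choice of 400.

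**Working it through.** **1. The plan's own figure.** The SAP gives no power or sample size for Aim 1b. Its primary-outcome figure (65% vs 76%, 284 per arm, Fisher's exact test, two-sided 0.05, power 0.80) reproduces as 0.799 by exact enumeration, but does not bear on this point.

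**2. Where the assay difference can act.**

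| Use of the cut-off | Intervention arm | Control arm | Can POC/laboratory disagreement act? |
|---|---|---|---|
| Entry | Initial POC test | First VL test up to and including 6 months | Yes, directly |
| 12-month outcome | POC; laboratory if POC missing | POC; laboratory if POC missing | Only through the fallback |

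The SAP gives like-for-like measurement in the two groups as its reason for moving to the 12-month outcome, and it keeps <40 as an a priori cut-off for that same outcome in Aim 1a.

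**3. Size of the fallback route at a cut-off of 40.** Approximately:

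bias = (difference between arms in share using the fallback) × (share above 40 by laboratory but below 40 by POC)

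Neither share is in the documents. I assume 0-20 points for the first and 5-20% for the second.

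- Equal fallback use: 0 × any share = 0.
- Middle case: 0.10 × 0.10 = 0.01, or 1 point.
- Upper end: 0.20 × 0.20 = 0.04, or 4 points.

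**4. Error rate if the better of two cut-offs could be picked.** Assumptions: no true effect; 50, 75 or 100 children per arm; pooled two-sided z-test at 0.05; 200,000 simulated trials per setting. The size of the Aim 1b subset is not documented. The SAP's expected 35% unsuppressed at 1000 gives 284 × 0.35 = 99.4 per arm, so 100 serves as a guide. Results at 100 per arm:

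| Assumed share <40 / <400 at 12 months | 400 alone | Better of 40 and 400 |
|---|---|---|
| 25% / 45% | 5.5% | 8.9% |
| 40% / 55% | 5.5% | 8.6% |
| 30% / 60% | 5.2% | 9.1% |
| 50% / 60% | 5.1% | 8.3% |

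Over all settings the ranges are 5.1-5.7% for 400 alone and 8.3-9.3% for the better of the two. Two independent tests would give 1 − 0.95² = 9.75%.

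A separate calculation used correlated normal statistics. Nested outcomes with shares p1 < p2 have correlation √[p1(1 − p2) / (p2(1 − p1))]. For 60% and 70% this is √(0.18 / 0.28) = 0.80, and the error rate was 7.8%. For 35% and 55% it was 8.5%.

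**5. Limit of step 4.** The simulation moves only the outcome cut-off in a fixed set of children, whereas the SAP moved entry as well. That changes the correlation between the two tests. Two tests each truly at 5% still cannot together exceed 10%.

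**The case against.** The change is not hidden: the changes section says it came after unblinding and names both uses of 400. The trigger it describes is paired enrollment samples, not 12-month results by arm. A reader might infer that 400 was picked because it gave a better answer; the documents do not say so, and only the timing is documented.

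A reader might also infer that the reason has no bearing on the outcome. That is too strong. The laboratory fallback lets the assay difference reach some 12-month values, and COVID-disrupted visits (reported especially at months 6 and 9) make some fallback plausible. There is a coherence argument too, though the SAP does not make it: once entry is at 400, achieving suppression is naturally judged at 400. The SAP elsewhere describes 400 as an operational threshold under updated Kenyan and WHO guidance, although it does not rely on that for Aim 1b.

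Nor should <1000 at 12 months be read as the protocol's outcome for these children, to be restored as the hypothesis test. The protocol planned time to suppression for them; 1000 was its general definition of suppression. Adding 1000 as a third option would raise the simulated error to 9.9-11.9%, but the documented move after unblinding was from 40 to 400 only.

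These points narrow the concern. They do not supply the missing label or show whether the result depends on the cut-off.

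**Conclusion.** The point holds as a fault of labelling and robustness in a secondary analysis. The Aim 1b section presents a cut-off adopted after unblinding as the analysis of its hypothesis, unlabelled, with no other cut-off planned. The stated reason supports the entry change well and the outcome change only through the fallback, worth 0 to 4 percentage points at a cut-off of 40 under the assumed shares and zero if fallback use is equal between arms. If the choice between 40 and 400 had been free, the 5% error rate could be about 8-9%. That is a hypothetical worst case resting on assumed suppression shares; it is neither an estimate of what happened nor evidence of selection on results. The primary outcome is unaffected.

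**What to change.** 1. In the SAP's Aim 1b text, state that the 400 cut-off for entry and outcome, and the subgroup analyses that use it, are post hoc, with a pointer to Changes to the analysis plan.
2. Report risk ratios and confidence intervals beside it as labelled sensitivity analyses with matched entry and outcome cut-offs: 40/40 (set before unblinding, with a note on its entry-classification bias) and 1000/1000 (the protocol's general definition of suppression). Matching matters: with entry at 400 and outcome at <1000, a child who stays between 400 and 999 throughout would count as having achieved suppression.
3. Give the number of 12-month laboratory-fallback results in each arm.
4. Make no confirmatory significance claim from the 400 analysis alone.

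The cost is a few lines of SAP text, two more model runs and one count, all on data already held.
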